5.3.1 Protocol Deviations Leading to Exclusion from the PP Analysis

Major protocol deviations leading to exclusion from the PP analysis will be reviewed and approved by Alnylam prior to database lock and unblinding of treatment assignments for all patients. This document of all major deviations will include a description of the deviation and the reason that the deviation demonstrates the need to exclude the patient from the PP population. Additional important protocol deviations leading to exclusion from the PP population may be identified during the study. The final document of major deviations will be finalized prior to database lock and unblinding of the treatment assignments for all patients.

The major protocol deviations leading to exclusion from PP population will be summarized by treatment group, and presented in a data listing.

At a minimum, the following criteria have been identified a priori as critical protocol deviations that will impact the co-primary efficacy endpoints and require exclusion from the PP population:

- Failure to meet one or more of the key inclusion/exclusion criteria (listed below)
- Receiving incorrect study drug for ≥1 administration
- Receiving <80% of scheduled doses or missed ≥ 6 consecutive doses

Key inclusion criteria:

- 1. Have a documented TTR mutation
- 2. Amyloid deposit in cardiac or non-cardiac tissue confirmed by Congo Red staining
- 3. Have a history of heart failure (HF) with at least 1 prior hospitalization for HF OR clinical evidence of HF that either requires/required diuretics or is/was associated with an NT-proBNP>400 ng/L or BNP>100 ng/L
- 4. Have evidence of cardiac involvement by Screening/Baseline echocardiogram including an end-diastolic intraventricular septum thickness of ≥ 12 mm. For patients with an end-diastolic intraventricular septum thickness of < 12 mm, an endomyocardial biopsy showing amyloid deposition is required.

- 5. Can walk \geq 150 meters on a 6-MWD test
- 6. Have a Karnofsky performance status of $\geq 50\%$

Key exclusion criteria:

- 1. Has known primary amyloidosis (AL), leptomeningeal amyloidosis, non-FAC hereditary cardiomyopathy, hypertensive cardiomyopathy or cardiomyopathy due to valvular heart disease.
- 2. Had a known peripheral vascular disease affecting amubulation
- 3. Had an acute coronary syndrome within the past 3 months.
- 4. Has a PND score>2
- 5. Has an NYHA classification of IV
- 6. Has received an investigational agent or device within 30 days of anticipated study drug administration or 5 half-lives of the investigational drug, whichever is longer.

7. Is currently taking diflunisal, tafamidis, doxycycline, or tauroursodeoxycholic acid; if previously on any of these agents, must have completed the 14-day wash-out prior to start of study drug administration.

6 DATA HANDLING

6.1 Time Points and Visit Windows

Day 1 will be defined as the day of first dose of study drug.

An evaluation date will be calculated relative to Day1 as follows:

- RelDay = (date of assessment date of first dose + 1) if collected after Day 1.
- RelDay = (date of assessment date of first dose) if collected prior to Day 1.

For analysis by visit, analysis windowing will be utilized for each scheduled visit such that unscheduled visits will also be considered. If there is more than one value within a visit window then the visit closest to the target day of the visit will be used in the analysis. If measurements are equally distant to the target day, then the later one will be used in the analysis. Details regarding the definition of the visit window will be summarized in a separate specifications document.

Baseline Definitions:

- For 6-MWD, baseline will be defined as the latest value prior to the first dose. If Day 1 assessment is not available, then the latest of the 2 screening 6MWD results will be selected to represent the baseline value for the patient in the analysis.
- For each of the PD parameters, baseline will be defined as the average of all measurements collected prior to the date of the first dose of study drug.
- For all other parameters, the baseline will be defined as the last assessment prior to the first dose
 of study drug.

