- g On Day 0 pre-dose, only interval medical history will be collected. Changes in medical history during the dosing period will be captured as treatment-emergent adverse events (TEAEs) or concomitant medication(s) as appropriate.
- h For the 12-lead ECG, each lead shall be recorded for at least 3 beats at a speed of 25 mm/s. Triplicate recordings will be obtained. The electrophysiological parameters assessed will be rhythm, ventricular rate, PR interval, QRS duration, QT interval, ST and T waves, Fredericia-corrected QT interval (QTcF), and Bazett-corrected QT (QTcB).
- i Vital signs include blood pressure, pulse rate, oral body temperature, and respiratory rate. Vital signs will be measured in the supine position after the patient has rested comfortably for 10 minutes. Vital signs should be collected at each site visit.
- j The pregnancy test will be performed for women of child-bearing potential (WOCBP) only. A serum pregnancy test will be performed at Screening/Baseline and urine pregnancy tests at all designated visits thereafter and anytime pregnancy is suspected. Urine pregnancy test may also be performed more frequently (monthly) based on local country requirements. The results of the pregnancy test at Screening/Baseline and the Day 0 pre-dose visit must be known prior to administration of study drug.
- k Coagulation studies include PT, aPTT, and INR.
- 1 Serology tests include HBsAb, HBsAg, and anti-HCV Ab.
- m eGFR will be calculated by the central lab and reported with the lab results.
- n BNP is only collected during Screening/Baseline. NT-proBNP, Troponin T and I are collected at each timepoint.
- o All samples should be taken within 1 hour pre-dose.
- Blood samples for anti-drug antibody testing will be collected prior to study drug dosing. A sample will be collected at the Early Termination visit, if applicable.
- q Where allowed per local regulations and IRB/EC approval, serum and plasma samples for exploratory biomarker testing will be collected.
- r Where allowed per local regulations, IRB/EC approval and patient consent, DNA sample will be collected.
- s PK will be assessed within 1 hour predose and 2.5±1 hour postdose.

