1.3. Summary of Clinical Data with ALN-TTRSC

Study ALN-TTRSC-001 was a Phase 1 randomized, double -blind, placebo-controlled study of ALN-TTRSC administration in healthy subjects. Subjects received single ascending doses or multiple ascending doses of up to 10 mg/kg or fixed doses of up to 600 mg of ALN-TTRSC, or placebo. In the multiple dose cohorts, subjects received a total of 10 doses over a 35 day period administered as 5 daily SC doses followed by 5 weekly doses.

In this study, ALN-TTRSC was generally well-tolerated. The majority of treatment-emergent adverse events (AEs) were mild or moderate in severity and considered unrelated to study treatment. There were no serious adverse events (SAEs). Injection site reactions (ISRs) were the most common AEs related to study treatment. All ISRs were mild or moderate in severity and resolved without sequelae. Overall, the incidence of alanine transaminase (ALT) and aspartate transaminase (AST) elevation >1× upper limit of normal (ULN) was similar in placebo and ALN-TTRSC-treated subjects. One subject who received 600 mg ALN-TTRSC developed an asymptomatic elevation of ALT (4.3×ULN) and AST (1.9×ULN), which was defined in the protocol as a dose limiting toxicity and resulted in study discontinuation. There were no other AEs leading to dose interruption or dose reduction. No elevations in cytokines, C-reactive protein, or other abnormal clinical findings were noted. The pharmacodynamic (PD) effect of ALN-TTRSC was dose-dependent and resulted in >85% reduction of TTR at ≥5 mg/kg of ALN-TTRSC and was accompanied by reduction of RBP and vitamin A. Fixed doses of 500 mg and 600 mg ALN-TTRSC also demonstrated similar safety and PD effect over a wide range of body weights compared to that observed in cohorts with weight-based dosing.

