7.3.2. Transthyretin

On scheduled visits, serum samples will be collected within one hour prior to dosing and analyzed for total TTR levels using an enzyme linked immunosorbent assay (ELISA) method at a central laboratory.

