9.2.5. Pharmacokinetic Analyses

Summary tables and graphical displays of observed values and changes from baseline in serum TTR will be used to assess the durability of suppression over the course of the study.

Plasma PK will be summarized and descriptive statistics conducted for each time point.

Inferential statistics of efficacy and PK/PD relationships will be conducted where possible.

PK-PD data will be analyzed via a population PK-PD model in order to leverage the sparse nature of the dataset. Details regarding the PKPD methods will be provided in a Pharmacokinetic Analysis Plan (PAP).

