1 SOURCE DOCUMENTS

The Statistical Analysis Plan (SAP) was written based on the following documentation:

Document	Date	Version
Protocol	03 October 2014	1.0
CRF	02 June 2015	6.0

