6.2 Handling of Dropouts or Missing Data

6.2.1 Efficacy Analysis

Patients who discontinue study drug prior to Month 18 will be encouraged to remain on the study and complete their remaining clinic visits through the 18-month visit. However it is possible that data will remain missing.

For the primary analysis of the co-primary efficacy endpoints, imputation of data will be performed if such cases occur:

- For calculation of eAUC (serum TTR), any assessment missing due to death or treatment discontinuation will be imputed using the baseline value, and thus the percent change at the visit will be 0%.
- If the serum TTR is recorded as "< value" then it will be imputed as half of that value (eg, TTR < 8.16 ng/mL will be imputed to be a value of 4.08).

For the primary analysis of the secondary efficacy endpoints, imputation of missing data will be performed if such cases occur:

- In the rare event that hospitalization dates are partially missing, imputation will be performed using the same approach as partial AE start dates (see Section 6.2.2).
- For KCCQ, missing responses to specific items will be handled in a manner consistent with standard patient reported outcome (PRO) scoring algorithms: a 50% proration rule will be applied to PRO data at the item level. Specifically, patients have to complete a minimum of half of the total number of items in each subscale to receive a valid subscale score; otherwise the subscale will not be scored. Missing scores at subscale level will not be imputed. Details of KCCQ scoring are described in Appendix III.

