7.6.1.3 Percent reduction in serum TTR from Baseline over 18 months

The primary analysis for the co-primary endpoint of percent change in TTR from baseline over 18 months will be analyzed using an Analysis of Covariance (ANCOVA) model.

The dependent variable used in the ANCOVA model w	rill be area under the effect curve (eAUC) to			
quantify the percent reduction in TTR from baseline over 18 months. The covariates used in the model				
will be treatment group, TTR mutation	and 6-MWD at Screening			
and baseline TTR serum levels. The	difference in the adjusted mean eAUC between			
treatment groups will also be presented with associated 95% confidence interval. The dependent variable				
will be log transformed.	-			

Calculation of eAUC will be based on trapezoidal method, where the y-axis is percent reduction in serum TTR and the x-axis is time since first dose of study drug. Assessments missing due to death or discontinuation will be imputed using the baseline value, and thus the percent change will be 0%. The span of time will start at time 0 (baseline) and end at month 18. Only scheduled visits will be included in the calculation of eAUC.

7.6.1.4 Sensitivity Analyses for Percent Reduction in Serum TTR from Baseline over 18 months

Sensitivity #1: Address impact of baseline factors

The eAUC will be analyzed using an unadjusted ANOVA model. The covariates of the model will be treatment group and the dependent variable will be eAUC.

Sensitivity #2: Address robustness using a different distributional assumptions

A mixed-effects model repeated	l measures (MMRM) ana	alysis based on the re	stricted maximum likelihood
(REML) method for estimation w	vill be performed for rela	tive fold change in s	serum TTR. The dependent
variable will be relative fold cha	ange defined as (TTR va	lue at follow-up visi	t/baseline TTR value). The
covariates used in the model wil	ll be treatment group, vis	sit, treatment group b	by visit interaction, TTR
mutation	and 6-MWD at Screeni	ng	and baseline
TTR serum levels. The difference	ce in the adjusted mean i	relative fold change	n serum TTR between
treatment groups and associated	95% will also be presen	ited. The dependent	variable will be log
transformed.			

Sensitivity #3: Address influence of missing data

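### The SAP's baseline rule for PD parameters excludes the only scheduled pre-treatment serum TTR sample, leaving the second co-primary without a defined baseline if TTR is a PD parameter

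*SAP*

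**What the plan says.** SAP 6.1 (Time Points and Visit Windows) has three baseline rules:

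- **6-MWD:** the latest value before the first dose, with a fallback to the screening tests.
- **PD parameters:** the "average of all measurements collected prior to the date of the first dose of study drug".
- **All other parameters:** the last assessment before the first dose.

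Only the PD rule sets its cut-off at the calendar date of the first dose. The other two set it at the dose itself.

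On sampling, footnote o to protocol Table 1-1 says of TTR: "All samples should be taken within 1 hour pre-dose". Protocol 7.3.2 agrees: "serum samples will be collected within one hour prior to dosing".

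On analysis, SAP 7.6.1.3 makes the area under the percent-reduction curve (eAUC) the dependent variable of an ANCOVA that also has baseline TTR as a covariate. The time span "will start at time 0 (baseline) and end at month 18", and only scheduled visits enter the calculation.

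**The concern.** A TTR sample drawn on the morning of the first injection would qualify under the 6-MWD rule or the general rule, but fails the PD rule. If that sample is the only one taken before treatment, a literal reading leaves TTR with no baseline.

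Baseline TTR enters the second co-primary twice, as the denominator of percent reduction and as a model covariate. It also enters the fold-change mixed model (SAP 7.6.1.4) and the subgroup ANCOVA (SAP 7.6.1.5). Unlike the 6-MWD rule, the PD rule has no fallback. If a few patients happened to have an unscheduled earlier sample, the literal rule would use that sample and discard Day 0 for them, and leave everyone else without a baseline.

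The imputation after death or discontinuation is not affected. SAP 6.2.1 fixes the result directly ("the percent change at the visit will be 0" percent), so it needs no measured baseline.

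**Working it through.** The plan states no figure to reproduce here. The check is a count of scheduled samples against each form of the rule.

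**Step 1: which day is the first dose?** Protocol 8.5 starts study drug on Day 0. SAP 6.1 labels the day of first dose Day 1. These are the same calendar day.

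**Step 2: when is TTR sampled?** I aligned the TTR row of Table 1-1 with the 27 column headers (Screening, Day 0 pre-dose, and so on to Week 82 and Early Termination). Because the table was read from PDF, I checked the alignment on other rows:

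| Row | Screening | Day 0 pre-dose |
|---|---|---|
| eGFR | marked | marked |
| NT-proBNP and troponins | marked | marked |
| Vitamin A | marked | blank |
| Plasma PK | blank | marked |
| **TTR protein** | **blank** | **marked** |

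The TTR row has 10 marks: Day 0 pre-dose, Weeks 4, 9, 13, 26, 39, 52, 65 and 78, and Early Termination. Scheduled samples without Early Termination: 10 − 1 = 9. Post-baseline scheduled samples: 9 − 1 = 8.

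**Step 3: apply the rules.** Footnote o and protocol 7.3.2 put the Day 0 sample within one hour before dosing, so its date is the date of first dose.

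| Cut-off | Scheduled TTR samples that qualify |
|---|---|
| Before the *date* of first dose (PD rule as written) | 0 of 9 |
| Before the first *dose* (form used by the other two rules) | 1 of 9, the Day 0 pre-dose sample |

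All 8 scheduled post-baseline percent reductions, and the ANCOVA covariate, depend on that one sample.

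**Step 4: is TTR a PD parameter?** The SAP does not say. Its Section 4 names no PD parameter and sends PK/PD analysis to a separate document. The evidence that TTR belongs here:

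- Protocol 1.3 describes TTR lowering as the PD effect: "The pharmacodynamic (PD) effect of ALN-TTRSC was dose-dependent and resulted in >85% reduction of TTR".
- Protocol 9.2.5, the pharmacokinetic analysis section, says that "changes from baseline in serum TTR will be used to assess the durability of suppression".
- The other candidates are placed elsewhere. SAP 3.4 treats vitamin A as a safety test, and SAP 7.7.8 only lists the exploratory biomarkers.

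**Step 5: is there another source of a baseline?** Exploratory biomarker samples at Screening may be tested for the mutant to wild-type TTR ratio (protocol 7.6.1). These depend on local rules and approval, and are not the scheduled total-TTR ELISA of protocol 7.3.2, so they do not supply one.

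**Step 6: does the SAP show its intent?** SAP 7.6.1.3 anchors the eAUC at time 0 and admits scheduled visits only. Under the supplied schedule that can only be the Day 0 pre-dose sample, which SAP 6.1 excludes.

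**The case against.** There are three serious arguments on the other side.

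*TTR may not fall under the PD rule.* The documents file it under efficacy: protocol 7.3.2 sits within Efficacy Assessments, and SAP 3.1, 6.2.1 and 7.6.1.3 all treat it as an efficacy endpoint. Under the general rule the Day 0 sample would qualify and nothing would be undefined. It stands that the PD label is an inference. But an efficacy endpoint can also be a PD parameter, and the protocol repeatedly calls TTR lowering the PD effect. If TTR was meant to fall elsewhere, the SAP still needs to say so.

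*The mismatch may come from comparing versions.* The SAP, issued 21 October 2015, was written from protocol version 1.0 of "03 October 2014" and CRF version 6.0 of 02 June 2015. Neither is supplied. The supplied protocol carries data as of January 2016, so it is later. Averaging several measurements suggests that the authors may have expected more than one pre-dose sample, perhaps from an earlier schedule, or it may be standard text. This stands as a limit: the conflict is shown only against the supplied schedule. It is also a reason to reconcile the two documents.

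*The practical effect is small.* Only one sensible scheduled value exists, so there is little room for a choice driven by results. No bias between arms and no change in type I error or power has been shown. This stands, and it limits how serious the point is. It does not make the written rule workable.

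**Conclusion.** The concern holds. Under the supplied schedule, and with TTR read as a PD parameter, the rule in SAP 6.1 admits 0 of 9 scheduled TTR samples as baseline, where 1 of 9 was evidently intended. Followed literally, it leaves the denominator and the covariate of the second co-primary undefined for every patient with scheduled samples only.

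The conclusion rests on two assumptions: that TTR belongs under the PD rule, and that the supplied schedule applies. Patients enrolled under an earlier schedule may differ. The wording and the sample count are certain. The consequence depends on both assumptions.

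This is an error in a stated rule, not a missing detail. It should be corrected before unblinding, so that the plan fixes the baseline of a co-primary endpoint and no programming decision is needed.

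**What to change.** Replace the PD bullet in SAP 6.1 with text to this effect: *for PD parameters, serum TTR among them, baseline is the mean of every value whose collection date and time precede the first injection; the pre-dose sample on protocol Day 0 (SAP Day 1) counts.*

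Finalise this before unblinding. When SAP Section 1 is brought up to date from protocol version 1.0, check the rule against the current schedule of assessments.

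The cost is one SAP bullet. It needs no new samples and no protocol amendment, and no data are lost.

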6.2 Handling of Dropouts or Missing Data

6.2.1 Efficacy Analysis

Patients who discontinue study drug prior to Month 18 will be encouraged to remain on the study and complete their remaining clinic visits through the 18-month visit. However it is possible that data will remain missing.

For the primary analysis of the co-primary efficacy endpoints, imputation of data will be performed if such cases occur:

- For calculation of eAUC (serum TTR), any assessment missing due to death or treatment discontinuation will be imputed using the baseline value, and thus the percent change at the visit will be 0%.
- If the serum TTR is recorded as "< value" then it will be imputed as half of that value (eg, TTR < 8.16 ng/mL will be imputed to be a value of 4.08).

For the primary analysis of the secondary efficacy endpoints, imputation of missing data will be performed if such cases occur:

- In the rare event that hospitalization dates are partially missing, imputation will be performed using the same approach as partial AE start dates (see Section 6.2.2).
- For KCCQ, missing responses to specific items will be handled in a manner consistent with standard patient reported outcome (PRO) scoring algorithms: a 50% proration rule will be applied to PRO data at the item level. Specifically, patients have to complete a minimum of half of the total number of items in each subscale to receive a valid subscale score; otherwise the subscale will not be scored. Missing scores at subscale level will not be imputed. Details of KCCQ scoring are described in Appendix III.

6.2.2 Safety Analysis

All safety analyses will be performed on observed data only. No missing data will be imputed except for partial dates of adverse events (AE) and concomitant medications (note: missing time will not be imputed).

Imputation rules for End Date of AE:

- If end date is completely missing, then end date remains missing (assume ongoing event)
- For a partial End date (day is missing, or month is missing or both day and month are missing) then the last day/month will be imputed.

Imputation rules for Start Date of AE:

- If start date is completely missing, then start date will be imputed to be the date of the first dose of study drug
- For a partial Start date (day is missing, month is missing or both day and month are missing):
 - partial date < the first dose date: the last day/month

- partial date = the first dose date: the first dose date
- partial date > the first dose date: the first day/month

If the imputed AE start date is after the imputed AE stop date, then the start date will be set to the imputed AE stop date.

For medications with partial start or stop dates: the first day/month will be imputed for start date, and the last day/month will be imputed for stop date.

For mediations with a completely missing start date, the medications will be considered as started prior to the first dose of study drug; medications will be classified as prior or concomitant depending on the medication stop dates. A completely missing stop date of medications will not be imputed and the medications will be assumed as ongoing.

Imputed dates will be used to determine if an adverse event is treatment-emergent, or a medication is a prior or concomitant medication. Imputed dates will not be listed in listings.

